6.3. Adverse Events of Special Interest (AEOSI)

In addition to analyses of AEs, adverse events of special interest (AEOSI) will be assessed. Definitions of AEOSI, as currently defined, are provided in Table 1, including but not limited to the listed. For AEOSI, frequency tables will be generated, showing overall summary of AEOSI, Summary of AEOSI by SOC and PT, Serious AEOSI by SOC and PT, AEOSI leading to study drug discontinuation by SOC and PT, AEOSI leading to dose modification by SOC and PT, Grade 3 or higher AEOSI by SOC and PT, treatment-related AEOSI (by a worst CTCAE grade of 3, 4, or 5, ≥ 3 and any grade) by SOC and PT. Corresponding listings will also be produced. Please see the lists at the end of this section for details.

Table 1: Definitions of Adverse Events of Special Interest

Adverse Event of Special Interest	Definition
Diarrhea	Preferred term: diarrhea
Neutropenia+	Preferred terms: neutropenia, neutrophil count decreased, febrile neutropenia
Febrile neutropenia	Preferred term: febrile neutropenia
Infections	SOC: infections and infestations
Neuropathy+	Preferred term: gait disturbance, hypoesthesia, muscular weakness, neuropathy peripheral, paresthesia, and peripheral sensory neuropathy
Hypersensitivity+*	Hypersensitivity SMQ (broad) and Anaphylactic Reactions SMQ (broad)*
Pulmonary events+	Interstitial lung disease SMQ (narrow)

All definitions based on MedDRA vs 20.0 or higher, SMQ=Standard MedDRA Query

+ Grouped AE terms

* For the category of Hypersensitivity+, only events whose onset dates are on the day of or 1 day after an infusion are included.

The following AEOSI tables will be provided:

- Overall Summary of Adverse Events of Special Interest
- Summary of Adverse Events of Special Interest by SOC and PT
- Summary of Serious Adverse Events of Special Interest by SOC and PT
- Summary of Adverse Events of Special Interest with NCI-CTCAE Grade 3 or Higher by SOC and PT
- Summary of Treatment-related Adverse Events of Special Interest with NCI-CTCAE Grade 3 or Higher by SOC and PT
- Summary of Adverse Events of Special Interest Leading to Dose Reduction by SOC and PT

- Summary of Treatment-related Adverse Events of Special Interest Leading to Dose Reduction by SOC and PT
- Summary of Adverse Events of Special Interest Leading to Dose Interruption by SOC and PT
- Summary of Treatment-related Adverse Events of Special Interest Leading to Dose Interruption by SOC and PT
- Summary of Adverse Events of Special Interest Leading to Study Drug Discontinuation by SOC and PT
- Summary of Treatment-related Adverse Events of Special Interest Leading to Study Drug Discontinuation by SOC and PT
- Summary of Adverse Events of Special Interest Leading to Death by SOC and PT
- Summary of Treatment-related Adverse Events of Special Interest Leading to Death by SOC and PT

The following AEOSI listings will be provided:

- Listing of Adverse Events of Special Interest
- Listing of Adverse Events of Special Interest with NCI-CTCAE Grade 3 or Higher by SOC and PT
- Listing of Treatment-related Adverse Events of Special Interest with NCI-CTCAE Grade 3 or Higher by SOC and PT
- Listing of Adverse Events of Special Interest Leading to Dose Reduction by SOC and PT
- Listing of Treatment-related Adverse Events of Special Interest Leading to Dose Reduction by SOC and PT
- Listing of Adverse Events of Special Interest Leading to Dose Interruption by SOC and PT
- Listing of Treatment-related Adverse Events of Special Interest Leading to Dose Interruption by SOC and PT
- Listing of Adverse Events of Special Interest Leading to Study Drug Discontinuation by SOC and PT
- Listing of Treatment-related Adverse Events of Special Interest Leading to Study Drug Discontinuation by SOC and PT
- Listing of Adverse Events of Special Interest Leading to Death by SOC and PT
- Listing of Treatment-related Adverse Events of Special Interest Leading to Death by SOC and PT

6.4. Death

All-cause deaths will be summarized (including presentation of causes of death), and deaths within 30 days of the last dose of study drug will be summarized. A listing of all death information will be generated.

6.5. Clinical Laboratory

Routine safety laboratories, based on hematology (including but not limited to hemoglobin, platelets, leukocytes, lymphocyte, neutrophils, monocytes, basophils and eosinophils) and routine serum chemistry data (including but not limited to glucose, creatinine, BUN, total bilirubin, AST, ALT, LDH, alkaline phosphatase, serum albumin, total protein, potassium, calcium, chloride, magnesium and phosphate), will be summarized using values at each visit and change from baseline using descriptive statistics. Laboratory test results for lab parameter including but not limited to platelets, neutrophils, white blood count, lymphocytes and hemoglobin will be graded according to NCI-CTCAE v5.0 severity grade. A shift table from baseline to the worst NCI-CTCAE grade observed on-treatment will be tabulated for each lab parameter. For parameters whose CTCAE scales do not exist, the proportion of subjects with abnormal values will be summarized.

Clinical laboratory data results will be reported in standard international units. Baseline is defined as the last observation occurring prior to the first treatment administration of sacituzumab govitecan.

If a lab value is reported using a non-numeric qualifier (e.g., less than [<] a certain value, or greater than [>] a certain value), the given numeric value will be used in the summary statistics, ignoring the non-numeric qualifier. Any other manipulation related to lab data and not documented here will be specified in the ADaM specification.

All lab values will be summarized by the single arm sacituzumab govitecan. If applicable, it may also be presented by dose level, cancer types and histology. Subgroup analysis may also be conducted for the lab parameters. The lab listings will be generated to support the lab tables.

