11.3.1. Endpoints

The primary endpoints are as follows:

- Percentage of participants experiencing any AE
- Percentage of participants experiencing any SAE
- Percentage of participants experiencing any laboratory abnormality

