11.3.3. Safety Analyses

Safety analyses will be based on All Treated Subjects. All safety analyses will be presented by cancer types and histology when deemed appropriate. Safety data will be summarized using descriptive statistics. Categorical variables will be summarized by number and percentage. Continuous variables will be summarized using n (number of subjects with available data), mean, standard deviation, median, upper and lower quartiles, and range (minimum and maximum), unless otherwise specified.

A treatment-emergent AE will be defined as any AE that begins on or after the date of first dose of study drug up to the date of last dose of study drug plus 30 days. Treatment-emergent laboratory abnormalities will be defined as values that increase at least 1 toxicity grade from baseline at any time after baseline up to and including the date of last dose of study drug plus 30 days. Treatment-emergent AEs and SAEs and clinical laboratory test results will be summarized. Study drug exposure and concomitant medications will also be summarized.

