1. INTRODUCTION

The purpose of this Statistical Analysis Plan (SAP) is to describe the procedures and the statistical methods that will be used to analyze, and report results for study IMMU-132-14: “Open-label Rollover Study to Evaluate Long-term Safety in Subjects with Metastatic Solid Tumors that are Benefiting from Continuation of Therapy with Sacituzumab Govitecan”. This SAP incorporates the original version of the protocol, dated as 16Dec2019. The focus of this SAP is for the final analysis specified in the study protocol.

This SAP provides a comprehensive and detailed description of the objectives, definitions of endpoints, statistical and analytical methods used to evaluate the specified safety endpoints. There is no efficacy analysis for this study.

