2. STUDY OBJECTIVES AND ENDPOINTS

2.1. Primary Objectives and Endpoints

The primary objective is to evaluate long-term safety in subjects with metastatic solid tumors that are benefiting from continuation of therapy with sacituzumab govitecan.

The corresponding endpoints are:

- Safety evaluated on adverse events and serious adverse events, laboratory assessments, study drug exposure and concomitant medications

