8. CHANGES TO ANALYSIS SPECIFIED IN PROTOCOL

Not applicable at this point.

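### The SAP reports laboratory data test by test, so it never produces the protocol's primary endpoint of subjects with any laboratory abnormality, and its on-treatment window has no stated end

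*SAP*

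**What the plan says.** Protocol 11.3.1 lists three primary endpoints. Two concern adverse events and serious adverse events. The third is "Percentage of participants experiencing any laboratory abnormality". Protocol 11.3.3 then defines treatment-emergent laboratory abnormalities as "values that increase at least 1 toxicity grade from baseline at any time after baseline", with the window running "up to and including the date of last dose of study drug plus 30 days". The same section bases safety analyses on All Treated Subjects and asks for numbers and percentages for categorical data.

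The SAP states its basis in Section 1: "This SAP incorporates the original version of the protocol, dated as 16Dec2019". Its Section 2.1 gives the endpoints as "Safety evaluated on adverse events and serious adverse events, laboratory assessments, study drug exposure and concomitant medications", with no laboratory percentage. SAP 6.5 plans four kinds of laboratory output:

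- descriptive summaries of values and changes from baseline, by visit;
- shift tables: "A shift table from baseline to the worst NCI-CTCAE grade observed on-treatment will be tabulated for each lab parameter";
- for ungraded tests: "For parameters whose CTCAE scales do not exist, the proportion of subjects with abnormal values will be summarized";
- supporting listings.

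SAP 6.5 defines baseline but not the end of the on-treatment period. SAP 7 does not mention laboratory data. SAP 8, on changes from the protocol, reads "Not applicable at this point".

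**The concern.** The third endpoint is a subject-level percentage pooled over tests: a subject counts once, whether one test or several are abnormal. None of the four planned outputs is that percentage. The gap is specific to laboratory data. SAP 6.2 plans an overall summary of treatment-emergent adverse events, which can carry the other two primary endpoints, and SAP 6.3 plans an overall summary for events of special interest.

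Two things are at stake. First, if the count is not planned, the definition, the window and the handling of ungradable subjects for a declared primary endpoint may be chosen after the data are visible, in an open-label single-arm study. Second, if on-treatment is taken to end at the last dose, the shift tables will disagree with the protocol's window of last dose plus 30 days.

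**Working it through.** The plan gives no figure to reproduce, so the check compares the sections and then asks whether the planned tables could yield the endpoint.

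**1. Endpoints against planned outputs**

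| Protocol 11.3.1 endpoint | SAP output that can give it |
|---|---|
| Any adverse event | Overall summary, SAP 6.2 |
| Any serious adverse event | Overall summary and serious-event tables, SAP 6.2 |
| Any laboratory abnormality | None |

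So 1 of 3 primary endpoints has no output in the SAP.

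**2. Could the single-test tables supply it?** Let p_i be the share of subjects with a grade rise on test i. Without knowing which subjects overlap, the pooled share is known only to lie between max(p_i) and min(1, Σp_i).

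- Two tests, assumed 40 of 200 subjects each: the lower bound is 40/200 = 20% and the upper bound is 80/200 = 40%.
- SAP 6.5 names 8 hematology and 15 chemistry tests, 23 in all. At an assumed 2% each (4 of 200), the range is 2% to 23 × 2% = 46% (92 of 200). Under independence it is 1 − 0.98^23 = 37%.
- At an assumed 5% each, the range is 5% to 100% (23 × 5% = 115%, capped). Under independence it is 1 − 0.95^23 = 69%.

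The rates are assumptions, and 200 is the planned maximum enrolment. The graded set may differ from 23, because the SAP list is open-ended and SAP 6.5 allows for tests without a CTCAE scale. The conclusion does not depend on these values: the endpoint needs its own subject-level count.

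**3. Where does on-treatment end?** The SAP's other sections point both ways.

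- To 30 days after the last dose: treatment-emergent adverse events (6.2) and one of the death summaries (6.4).
- To the last dose: treatment duration (6.1). Newly started concomitant medications also count only if begun before the last dose (5.5.1).

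Two kinds of sample depend on the answer.

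- *End-of-treatment sample.* Hematology and chemistry are required at this visit (Protocol Table 1, footnotes c and d), about 30 days after the last dose (Protocol 3.4). A window ending at the last dose excludes it. The protocol's window includes it up to day 30 and excludes it from day 31.
- *Pre-dose sample at a visit where dosing stops for good.* On the nominal 21-day cycle, it falls 8 − 1 = 7 days after a Day 1 dose, or 22 − 8 = 14 days after a Day 8 dose. Both are inside 30 days. Protocol Table 2 also lists stopping after a delay beyond 3 weeks. For a Day 1 dose due 14 days after Day 8, that decision visit comes more than 14 + 21 = 35 days after the last dose, outside the window.

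**4. Any against treatment-emergent.** Protocol 11.3.1 says *any*, 11.3.3 defines *treatment-emergent*, and neither section equates them. A grade present at baseline and unchanged counts under a literal *any* but not under the grade-rise rule. An out-of-range result on an ungraded test also counts under a literal *any*, but has no grade that could rise. The documents give no rate of baseline abnormalities, so this difference cannot be sized.

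**The case against.** The strongest reply is that this is version lag with little consequence. The current protocol already names the endpoint, population, grade rule, window and n (%) format, and the SAP was written to an older protocol. Off-diagonal cells of each shift table show grade rises for that test. Listings would let a programmer derive the pooled count, and SAP 6.5 refers undocumented laboratory data handling to an ADaM specification. The study is descriptive, sized on expected rollover, and no test depends on this percentage.

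Much of that stands: the consequence is modest and the cause is probably the version difference. It does not close the gap. The shift-table cells give single-test counts only, and only once the window is fixed. SAP 6.5 leaves data handling to the ADaM specification, which is not among the documents; it does not assign it an additional primary result.

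A reader might infer several stronger points that the documents do not support:

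- *The denominator is open.* Protocol 11.3.3 and SAP 5.1 both set All Treated Subjects. What is missing is narrower: how to classify a subject with no gradable baseline or post-baseline value.
- *Every sample at a stopping visit falls within 30 days of the last dose.* The delay case above shows otherwise.
- *The protocol's window secures the end-of-treatment sample.* That visit is only approximately 30 days out, so later samples still need a rule.
- *A safety signal is lost.* The data are collected, and a result that changes dosing is also an adverse event (Protocol 10.2.2.8).
- *SAP 8 is wrong.* The original protocol is not available to compare. The section is out of date against the current protocol, and no more can be said.

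**Conclusion.** The point holds and should be corrected before the analysis. Following the SAP as written does not produce one of the three primary results, and the planned single-test tables cannot yield it. The undefined on-treatment period can also put the shift tables at odds with Protocol 11.3.3. The harm is an unplanned primary result and a possible mismatch between documents; no information is lost.

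The omission and the missing window rest on the text alone. The pooled ranges rest on assumed rates and serve only to show that the endpoint cannot be derived. Part of the ambiguity, *any* against *treatment-emergent*, lies in the protocol itself, so a SAP change alone would not fully resolve it.

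**What to change.** 1. Update SAP Sections 1, 2.1 and 8 to the current protocol and its three primary endpoints.
2. Add one table to SAP 6.5: n (%) of All Treated Subjects with at least one treatment-emergent laboratory abnormality in any graded parameter, using the Protocol 11.3.3 grade-rise rule and window and including unscheduled values.
3. Use the same window for the shift tables, in place of the undefined on-treatment period.
4. State how end-of-treatment samples taken after day 30 are handled, and how subjects with no gradable baseline or post-baseline value are classified.
5. Reconcile *any* in Protocol 11.3.1 with *treatment-emergent* in 11.3.3, in the protocol as well as the SAP, and say whether ungraded tests count. The choice is the sponsor's. If a literal *any* is intended, the table in item 2 changes accordingly.

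Cost: a short SAP amendment, a protocol wording clarification and one more table. No new data are needed.

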7. METHODS FOR HANDLING MISSING DATA

The imputation for missing data in adverse events, concomitant medications and other prior therapies/procedures will be provided in a separate file.

8. CHANGES TO ANALYSIS SPECIFIED IN PROTOCOL

Not applicable at this point.

